### **13) Participant timeline**

In patients who are eligible for DOT there is concern about adherence and potential loss to follow up. In a clinic setting DOT is therefore generally set up and arranged during the clinic appointment during which it is first discussed. We wish to mirror this rapid service in the trial and therefore will aim to complete recruitment during the clinic session at which DOT is first discussed with the patient. This will also minimise loss to follow up prior to being able to establish the intervention. Randomisation into the treatment groups is balanced on the stage of treatment at enrolment, thus the length of time on DOT prior to enrolment should not differ between groups, but should there be any imbalances this will be controlled for in the analysis.

In order to meet the needs of participating clinics and allow this rapid recruitment over multiple sites there are three options for recruitment:

A) When clinics first join the study, study nurses will attend outpatient clinics and be able to recruit patients referred by the clinic nurse through a face to face meeting. Clinic nurses will be encouraged to observe as part of their training in recruitment. Study nurses may also attend clinic if they are given advance warning that a patient who is eligible for DOT (or already on DOT) will be at clinic.

B) When study nurses are not available on site, and clinic resources permit, clinic nurses will: explain the study; provide study information; seek consent; randomise the patient; complete the baseline questionnaire with the patient (largely populated from existing data collected during the course of routine care) and liaise with the study team to organise follow up.

C) When study nurses are not available on site and there are insufficient clinic resources to recruit patients directly, the clinic nurse will arrange a video conference with the study team who will: discuss the study with the patient; seek written consent; randomise and arrange onward follow up. The clinic nurse will complete the baseline questionnaire (largely populated from existing data collected during the course of routine care).

Day zero. Time zero – Clinic identifies patient eligible for DOT during outpatient or inpatient episode. (A, B, C)

Day zero. Time 0-5 mins – Clinic nurse discusses the recommendation that the patient be treated with DOT and the possibility of being involved in a study of how best to observe treatment (face to face) or using video observed therapy. (A, B, C)

Day zero – Time 5-25 minutes - Clinic nurse provides patient information sheet to patient and allows them to assess whether they wish to receive further information. (A, B, C)

Day zero – Time 25-50 minutes –Clinic nurse (A) or study nurse (B or C) explain the study, seek written consent, randomise and arrange onward care.

Day zero – Time 50-60 minutes - study nurse (A) or clinic nurse (B, C) collect baseline data largely populated from existing clinical data/care records.

Day zero Time 60 minutes -120 minutes (A & B) – Training in use of VOT and provision of smart phone.

Day one (or first working day after day zero) – (C) VOT training up to 1 hour at patients home or at clinic depending on patient preference.

Day one (A & B) or two (C) – VOT arm – patient attempt to submit VOT clip unaided, study team liaises and arranges further training if necessary.

Day one (or first scheduled DOT appointment) – patient begins attending for DOT.

[figure not shown]
0-2 months – regular DOT/VOT with adherence data collection and monitoring of side effects.

2 months – Study team contact participant by telephone to complete follow up questionnaire covering satisfaction with DOT or VOT, Time spent on DOT or VOT, Employment and quality of life, periods of time spent away from home.

Regular out-patient appointment closest to 2 months clinic nurse requests sputum sample to test for culture conversion at local laboratory.

6 months or end of treatment - Study team contact participant by telephone to complete end of follow up questionnaire covering satisfaction with DOT or VOT, Time spent on DOT or VOT, Employment and quality of life, periods of time spent away from home. For patients still requiring onward care the study will liaise with the clinic and Find&Treat to organise continuing DOT or VOT.

Schematic of participant timeline

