**8) Description of trial design.**

The TB Reach VOT trial is designed as a randomised, controlled, analyst blinded multicenter superiority trial with two parallel groups (VOT and DOT) with a 1:1 allocation and a primary endpoint of 80% of doses being observed over a 2 month period.

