## **Methods: Participants, interventions, and outcomes**

**9) Description of study settings:** Tuberculosis outpatient clinics in London and Birmingham and the London TB outreach service: Find&Treat.

**10) Inclusion criteria:** Any patient 16 years of age or older eligible for DOT at participating clinics regardless of whether the patients have previously agreed to treatment observation.

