#### **14) Sample size:**

A widely used programmatic measure of acceptable adherence is that patients are known to have taken at least 80% of their scheduled doses. This is particularly important early in treatment. We therefore define an adherent patient as one who is observed to take over 80% of their treatment and will compare the proportion of patients who are adherent in each arm over the first 2 months from randomisation as the primary outcome.

We have examined the power implications of a range of realistic differences in the primary outcome with 90% power at the 5% significance level (2 sided) with equal numbers in intervention and control arms of a superiority trial (table 1).

We have reviewed adherence data from Cohort review of TB patients and the VOT pilot and this suggests the 3rd or 4th scenarios are realistic.

Table 1 – Sample size needed at differing estimates of adherence and effect size.

	50% vs 70%	40% vs 60%	65% vs 80%	60% vs 75%
Intervention	121	126	181	200
Control	121	126	181	200
Total	242	252	362	400

We will aim to recruit 400 participants into the trial over a two year period.

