#### **15) Recruitment Strategies for achieving adequate participant enrolment to reach target sample size.**

Recruitment relies on conducting the study in multiple centres. We have focussed recruitment of clinics based on existing good relationships and high numbers of cases eligible for DOT. We are also approaching Birmingham clinics to increase numbers.

Based on the following assumptions we expect to be able to recruit 400 patients over a 2 year period.

Assumptions:

The annual number of eligible patients at each clinic will be similar to the annual number of patients reported to national enhanced surveillance in 2010 and 2011 as having social risk factors (homelessness, problem drug or alcohol use or history of imprisonment) but not on DOT, plus the number of patients already on DOT. This averaged at 420 eligible per annum.

It was also assumed that:

95% of those eligible for DOT are also eligible for the trial

Clinics attempt to recruit 75% of those eligible

2/3 of those who are approached agree to participate (based on pilot data VOT acceptance rates)

Note – As MDRTB patients with twice daily treatment are now not included in the randomisation we have not included MDRTB in the estimates. The true numbers of eligibles will be higher as we have ignored, previous history of TB and history of poor adherence, also this is based on incident eligible cases whereas we will also be recruiting patients who are currently on DOT.

We will initially attend outpatient appointments to induct clinics and promote the trial. We will visit clinics monthly for quality control visits.

Another strategy for achieving good recruitment is an emphasis on recruiting patients on the day the study is first introduced to them. As this is a hard – to – engage group delaying this could lead to substantial drop-out.

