## **Methods: Assignment of interventions (for controlled trials)**

Allocation:

16a) Sequence generation

We will use computer generated randomisation by minimisation to ensure balance across study sites and stage of treatment at which recruitment took place 1) at start of treatment; 2) after start but within first 2 months of treatment; 3) After first 2 months of treatment.

This will ensure that treatments are balanced within the two strata.

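### Section 13 infers equal prior time on DOT from balance on stage of treatment; the inference does not hold, and the promised adjustment is only conditional

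*Protocol*

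**What the plan says.** Section 16a of the protocol minimises to secure "balance across study sites and stage of treatment at which recruitment took place". Stage has three levels: at the start of treatment, after the start but inside the first two months, and later than two months. DOT status at entry is not a factor.

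Section 13 draws a conclusion from this: "thus the length of time on DOT prior to enrolment should not differ between groups". The same sentence adds that any imbalance that does arise will be dealt with at analysis.

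Three places show how varied DOT history at entry can be. Section 10 admits anyone aged 16 or over who is eligible for DOT, "regardless of whether the patients have previously agreed to treatment observation". Section 15 builds the eligible pool from patients with social risk factors who are not on DOT together with those who are, and notes that "this is based on incident eligible cases whereas we will also be recruiting patients who are currently on DOT". Section 13, recruitment option A, also foresees recruiting people already on DOT.

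On analysis, section 20a compares categorical outcomes with a chi-square or Fisher test. Section 20b allows adjustment as a secondary analysis, for variables that are unbalanced and associated with outcome. It also foresees interaction terms for possible effect modifiers.

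**The concern.** Time since the first dose and time under observation are different quantities. Take three patients recruited ten weeks into treatment. One has been on DOT throughout, one has self-administered and is only now referred, and one was offered DOT and did not agree. All three fall in the same stage stratum and minimisation treats them alike. Balance on stage therefore does not deliver balance on prior DOT.

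This matters because DOT status at entry could plausibly relate to the primary outcome, which is completing more than 80% of scheduled sessions over two months. For someone already on DOT, one arm continues an existing routine and the other changes it. If the team relies on the statement in section 13, it has less reason to record DOT status before allocation or to plan an adjustment for it. The fallback it would then depend on is weaker in section 20b than section 13 suggests.

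**Working it through.** **1. The protocol's own figures.** Table 1 is set "with 90% power at the 5% significance level (2 sided) with equal numbers in intervention and control arms of a superiority trial". With n per arm = [p1(1−p1) + p2(1−p2)] × (1.960 + 1.282)² / d²:

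- 60% vs 75%: (0.2400 + 0.1875) × 10.51 / 0.0225 ≈ 200 (stated 200)
- 65% vs 80%: (0.2275 + 0.1600) × 10.51 / 0.0225 ≈ 181 (stated 181)
- 50% vs 70%: 121 (stated 121)
- 40% vs 60%: 126.1, or 127 when rounded up (stated 126)

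The recruitment forecast in section 15 also reproduces: 420 × 0.95 × 0.75 × 2/3 × 2 years = 399, against a target of 400. Nothing below changes these figures.

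**2. What stage can and cannot balance.** At the start of treatment there is little or no earlier DOT to balance. In the second stratum, DOT during the current treatment is capped at two months but can be anything from none up to that cap. In the third it can range from none to the whole treatment so far. Stage limits prior DOT time from above and does not fix it. The mixing by DOT exposure is mainly in strata 2 and 3.

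**3. Size of the chance imbalance.** The protocol does not give the share s of participants already on DOT, so 20 to 40% is assumed. With 200 per arm and allocation unrelated to DOT status, SD of the between-arm difference = 2 × √(s(1−s)/400):

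| s | SD (percentage points) |
|---|---|
| 0.20 | 4.0 |
| 0.30 | 4.6 |
| 0.40 | 4.9 |

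**4. Check by simulating the minimisation.** Assumptions not in the protocol: 20 sites; stage shares of 40/30/30%; allocation to the favoured arm with probability 0.8; 0 to 10% on DOT in stratum 1 and 30 to 70% in strata 2 and 3; success of 75% if on DOT and 55% if not; no treatment effect; 1,000 runs for each of three scenarios.

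| Minimisation factors | Mean imbalance | SD (points) | 95th percentile of absolute imbalance (points) | Type I error, unadjusted test |
|---|---|---|---|---|
| Site and stage | 0 | 3.6–4.2 | 7.0–8.0 | 4.4–5.6% |
| Site, stage and DOT status | 0 | 0.6–0.7 | 1.2–1.5 | 3.8–4.1% |

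Balancing stage brings the SD a little below the formula in step 3, because stage and DOT status are related. Adding DOT status as a factor nearly removes the imbalance. The Monte Carlo standard error of a 5% rate over 1,000 runs is √(0.05 × 0.95/1000) ≈ 0.7 points, so all the values in the first row are compatible with 5%.

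**5. What this could do to the estimate.** Suppose success differs by 20 to 50 points between patients on DOT and the rest. This gap is assumed, as the protocol gives no adherence rates by DOT status. The 95% range of the shift is then 1.96 × SD × gap:

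- smallest: 1.96 × 4.0 × 0.20 ≈ ±1.6 points
- largest: 1.96 × 4.9 × 0.50 ≈ ±4.8 points

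For scale, the planned difference is 15 points. The standard error at 60% vs 75% with 200 per arm is √((0.2400 + 0.1875)/200) ≈ 4.6 points, a 95% half-width of about ±9.1. The shift is a component of that half-width and does not add to it.

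**6. The fallback.** Section 13 promises control of any imbalance without conditions. Section 20b requires both observed imbalance and an association with outcome, and places the adjustment in a secondary analysis. Section 20a leaves the main comparison unadjusted. Whether adjustment happens at all therefore depends on the data.

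**The case against.** The strongest reply is that randomisation already does the necessary work. DOT status is balanced in expectation, the unadjusted test keeps its error rate, and the variation in step 5 is already carried by the planned confidence interval. Section 13 does not claim perfect balance, since it goes straight on to promise adjustment, and section 20b foresees interaction tests. Stage also does part of the job, because it caps time on DOT in the first two strata. All of this stands, and it limits the point to a wrong rationale and a loose fallback.

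It can also be said that DOT status may already be on the randomisation form or baseline CRF (Appendices 6 and 8). These are not shown, and section 18a says baseline data cover the reasons for DOT eligibility. So the protocol cannot be said to leave DOT status unrecorded. Its text does not name it.

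A reader might infer more: that patients who had not agreed to DOT would tilt the trial towards VOT, since section 11b scores failure to take up the allocated method as failure. The protocol does not support treating that as a flaw. Enrolling these patients is deliberate (section 10), the failure rule applies to both arms, and different uptake is part of the effect that an intention-to-treat comparison is meant to capture. Minimising on DOT status would not alter it. Nor can the two-thirds figure in section 15 be used to size it, because that is agreement to join the trial and not uptake of VOT after allocation. The exclusion of patients unsuitable for VOT applies before randomisation to both arms, so it bears on generalisability and not on balance.

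**Conclusion.** The point holds in a limited form. The inference in section 13 is wrong, because balance on stage of treatment does not secure balance on prior time on DOT once treatment has started. The consequence is chance imbalance with an SD of about 4 to 5 points in the share already on DOT, given 400 participants and an assumed share of 20 to 40%. It is not bias, and no sample size or error rate in the protocol is shown to be wrong.

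A reader might go further and call DOT status an uncontrolled factor, or the main prognostic split at entry. Neither reading is supported. Randomisation controls it in expectation, section 13 promises adjustment, and the protocol contains no outcome rates by DOT status. What remains is that the adjustment promised in section 13 is narrower in section 20b, where it is secondary and depends on the data. A cheap change would secure the balance that section 13 says it already has.

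**What to change.** - Section 13: remove the inference from stage of treatment to time on DOT. State that the two are different and that DOT status is balanced separately.
- Randomisation form: record DOT status before allocation in three categories (currently on DOT; not yet offered; offered and not agreed), if it is not already there. The timeline in section 13 puts baseline data collection after randomisation, so an item held only on the baseline form would be completed by staff who already know the arm.
- Section 16a: add DOT status as a third minimisation factor.
- Section 20: adjust for DOT status by pre-specification, and not only when imbalance is seen, and bring section 20b into line with section 13.
- Optionally, list DOT status among the effect modifiers that section 20b already foresees.

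The cost is one field in the central randomisation system and a few sentences of text. The downside is slightly looser balance across sites. The expected gain is a modest improvement in balance and precision. The sample size does not change.

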## **Methods: Data collection, management, and analysis**

### **18a) Data collection methods**

Recruitment data (CRF 1 - Appendix 7): Recruiting clinics will collect anonymous data on the characteristics of patients who were approached for the trial but declined to participate using a study recruitment log sheet. This will include age, sex and factors that make them eligible for DOT.

Baseline Data (CRF 2 – Appendix 8): Study or clinic nurses will collect baseline data at the time of initial recruitment. This mainly consists of data already routinely collected by clinics, covering patient demographics, disease categorisation and factors that make them eligible for DOT. It will also include the validated EQ-5D quality of life scale and information on employment status and approximate weekly salary

VOT/DOT diary (CRF 3 – Appendix 9):

This will be recorded by the DOT observer at the time of the scheduled session and by the VOT observer at the time of reading scheduled video clips. DOT/VOT observers will be trained to complete (CRF 3 – see section 18a) consistently. CRF3 will be faxed/emailed on a weekly basis to the study centre with the study centre following up with DOT observers when weekly forms are not returned. CRF3 will be completed directly at the study centre on the VOT reading system.

The VOT reading system includes: fields to identify when doses are scheduled; when clips are submitted and read and the following categorisation of clips:

Patient took meds?

- Y (Yes, all meds)
- P (Probably)
- S (Yes, some meds)
- N (No meds taken)
- U (Unable to tell)
- DNA / Did not send clip

This data will be used for the primary outcome and secondary adherence outcome measures.

The system also collects additional data on video and audio quality. The system collects data on geo-location at the time of recording. This will be collected if the participant provides separate consent for this.

DOT: A DOT diary will be completed by DOT observers showing when doses are scheduled to be observed, whether or not the participant attended, when they attended and whether they took the medicines categorised as above.

Patient 2 and 6 month follow up (CRF 4a & 4b – Appendix 10): The study team will contact the participant by telephone to complete a 5 minute questionnaire covering

- Quality of Life (EQ5D)
- Participant satisfaction (Likert scale)
- Participant resource use for DOT/VOT (Participant time, missed work)
- Employment
- Hospitalisation

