## **27) Confidentiality**

Information on potential trial participants will be collected in anonymous form.(CRF1)

All other CRFs will be identified using the unique participant id allocated at randomisation.

The master data file will be stored on a UCL password protected network with access restricted to study personnel. This will be backed up automatically on a daily basis. The master data file will use the unique study number allocated at the time of randomisation but will not include personal identifier information. This identifiable information will be held in a separate password protected file on the same network drive in the form of a look up table.

Study sites will also maintain separate look up tables on NHS password protected computers.

All data analyses will be conducted on anonymised data with no identifiable data leaving the study site. Analyses will be reported at a level preventing deductive disclosure.

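### The self-reported baseline items (EQ-5D, employment, salary) are collected after randomisation in an open-label trial, so they may not be true pre-allocation values

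*Protocol*

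**What the plan says.** Section 13 (Participant timeline) sets out day zero by the minute. At minutes 25-50 a nurse is to "explain the study, seek written consent, randomise and arrange onward care". At minutes 50-60 a nurse is to "collect baseline data largely populated from existing clinical data/care records". Both steps apply to routes A, B and C.

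The descriptions of the routes earlier in the same section agree. Under route B the clinic nurse will "seek consent; randomise the patient; complete the baseline questionnaire with the patient". Under route C the study team, by video conference, will "seek written consent; randomise and arrange onward follow up. The clinic nurse will complete the baseline questionnaire". The description of route A gives no order of its own, so for route A the minute-by-minute list governs.

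Section 18a says that CRF 2 consists mainly of routine clinic data, and then adds: "It will also include the validated EQ-5D quality of life scale and information on employment status and approximate weekly salary". Section 12 lists EQ-5D and employment among the secondary outcome measures that the study collects directly at baseline, and by telephone at 2 and 6 months. Section 17a states that participants and care providers cannot be blinded.

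**The concern.** A baseline value earns its place in an analysis because allocation cannot have influenced it. Items read from clinic records largely keep that property whenever they are transcribed. A self-report given after an open allocation does not. The two arms ask very different things of a participant: section 6 describes DOT as needing at least three visits a week, while VOT supplies a smartphone and asks for video clips. Learning which of these lies ahead could colour the answers to EQ-5D, and the nurse who records them would know the arm too. Employment and salary share the weakness to a lesser degree.

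At stake are the uses of these items as baselines: the check that randomisation balanced the arms, any covariate adjustment that follows from it, and any quality-of-life or cost-effectiveness result expressed relative to baseline. No later analysis can recover a pre-allocation answer that was never taken.

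**Working it through.** The protocol gives no figure to reproduce here. The check is on the order of steps, followed by simple algebra for the consequence.

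**1. Is the order fixed?**

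| Place in protocol | What it implies |
|---|---|
| Section 13, minutes 25-50 | consent and randomisation, all routes |
| Section 13, minutes 50-60 | baseline data, all routes |
| Section 13, route B | "randomise the patient; complete the baseline questionnaire with the patient", in that order |
| Section 13, route C | randomisation listed first, baseline form next |
| Section 18a | "Study or clinic nurses will collect baseline data at the time of initial recruitment": compatible with either order |
| Section 27 | "All other CRFs will be identified using the unique participant id allocated at randomisation": CRF 2 has no identifier until randomisation |

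The order is explicit, and nothing contradicts it. Section 27 corroborates it.

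**2. Is the arm known when EQ-5D is answered?** No sentence says so. The supports are:
- the lack of blinding (17a);
- the clinic obtaining the allocation, or being told it, at randomisation (16b);
- onward care being arranged in the same step as randomisation (13);
- VOT training starting at minute 60 under routes A and B (13).

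Nothing holds the allocation back until the form is complete. This is a strong inference, but still an inference.

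**3. Which items are exposed?** Section 18a names EQ-5D, employment status and approximate weekly salary as additions to the routine data. Record-derived items are unlikely to be affected.

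**4. What does a shift do?** Let τ be the true between-arm difference in mean follow-up EQ-5D. Suppose that learning the arm raises the recorded baseline in one arm by d relative to the other and leaves follow-up unchanged.
- Comparison of follow-up values only: estimate = τ, so bias = 0.
- Change from baseline: estimate = τ − d, so bias = −d.
- Adjusted for baseline with within-arm slope β: estimate = τ − βd, so bias = −βd.
- Balance check: expected difference = d, where randomisation alone would give 0.

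The protocol supplies neither d nor β. With the assumed values d = 0.02 to 0.05 and β = 0.5:

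| d | Bias, follow-up only | Bias, change score | Bias, adjusted (0.5 × d) |
|---|---|---|---|
| 0.02 | 0 | −0.02 | −0.01 |
| 0.05 | 0 | −0.05 | −0.025 |

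If d = 0, every entry is zero.

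**5. Where would baseline values enter the stated analysis?** Section 20a compares continuous outcomes between arms with the Wilcoxon rank-sum test and names no change score. It also compares baseline characteristics between arms. Section 20b then adjusts, in secondary analysis, for variables that are unbalanced and associated with outcome. The cost-effectiveness objective in section 7 has no stated method. The documented routes are therefore the balance check and the conditional adjustment. Change scores and cost-effectiveness are possible routes only.

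**The case against.** The strongest reply is that the stated analysis hardly uses the exposed quantity. A rank-sum comparison of follow-up EQ-5D ignores the baseline, adjustment is secondary and conditional, and the protocol mentions neither a baseline-adjusted EQ-5D model nor quality-adjusted life years. That stands, and it limits the point to the uses listed above.

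The reply continues that most of CRF 2 comes from records, and that EQ-5D is asked within minutes of allocation, before VOT training and before any dose observed in the allocated arm. Both are true. The first narrows the point to three items. The second makes a large shift less likely but does not rule one out.

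Three stronger readings are tempting, and the documents do not support them:
- A reader might infer that the trial's quality-of-life comparison is biased as it stands. It is not, if follow-up values are compared without adjustment.
- A reader might take 0.02 to 0.05 as an estimate of the bias. It is an assumption with no source in the protocol.
- A reader might infer that people who leave on learning their arm will create informative gaps in baseline EQ-5D. This is possible in principle, since section 11b foresees participants not taking up the allocated offer. But no rate is given, such people would probably lack follow-up EQ-5D as well, and section 11b counts them as failures rather than dropping them.

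**Conclusion.** The point holds for three self-reported items. The protocol fixes baseline collection after randomisation in all three routes, and EQ-5D, employment status and salary are very probably answered with the arm known. This could bias the baseline balance check, the adjustment for unbalanced variables, and any change-from-baseline or baseline-adjusted quality-of-life or cost-effectiveness result. A difference caused by reaction to allocation could be mistaken for chance imbalance and then adjusted for.

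The primary outcome, the sample size and an unadjusted comparison of follow-up EQ-5D are untouched. The size of any shift is unknown. The conclusion rests on one inference, that the participant learns the arm during the randomisation step, and on the assumption that learning it can alter the answers. The point merits correction because the weakness is avoidable at little cost, not because serious bias has been shown.

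**What to change.** - In section 13, in both the route descriptions and the day-zero list, place EQ-5D, employment status and weekly salary after consent and before randomisation for routes A, B and C. Record-derived items can stay where they are.
- In section 18a, replace the loose statement of timing with the same order.
- In section 16b and on the randomisation form, add completion of the self-reported baseline items to the consent and eligibility checks that the system already makes before it allocates.
- In section 27, allow a temporary pre-randomisation number for these items, linked to the study ID once it is issued.

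The cost is small but not nil. A temporary identifier and its linkage must be managed. Under route C the video call must pause briefly while the clinic nurse completes the three items. Section 13 allots 10 minutes (50 to 60) to the whole baseline form, so moving part of it need not lengthen the visit, and same-day recruitment is kept.

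The same edit is a chance to reconcile who obtains consent and randomises. The route descriptions give this to the study nurse under A and the clinic nurse under B, and the day-zero list gives it the other way round.
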